6.5. Study Intervention Compliance

Compliance with study intervention will be assessed at each visit including the digital visits.

- At inclusion, the participant will be instructed to keep a drug-diary, either on a paper-form provided by study personnel or optionally electronically in their own calendar or with the RheumaBuddy® app.
- At each visit (every two months), the participant will fill in the dates of the drug injections since the last visit in a calendar and fill out a questionnaire assessing compliance into the eCRF. See Appendix 17 for wording of the questions. The questionnaire will be provided in the primary language of each country.

- Before adjusting the dosage according to the trial protocol, study personnel will call the participant and ask if they have taken the drug as prescribed the last four weeks. Deviations from the prescribed dosage regimen will be recorded in the eCRF, including the reason for deviation.

6.6. Other Dose and Schedule Modification

Modification of dosing regimens related to abnormal blood values and/or AEs should be performed based on the SmPC, clinical judgment and if necessary, contact with the study lead. If a TNFi dose is delayed due to non-RA related factors such as infections, surgery, vacation, subject non-compliance etc. this should be recorded and the reason given in the eCRF.

6.7. Continued Access to Study Intervention after the End of the Study

Participants will return to standard of care.

6.8. Treatment of Overdose

Not applicable.

6.9. Prior and Concomitant Therapy

6.9.1. Prior Therapy

All prior use of disease-modifying drugs/immunosuppressive therapy (excluding corticosteroids and NSAIDs) will be recorded in the eCRF with specification of both the time (month and year) of treatment start and time of termination (month and year) of biological drugs. If known, the reason for termination of prior biological therapy (i.e., lack of efficacy, loss of efficacy, side effects, development of ADAbs, or other) will be recorded.

6.9.2. Concomitant Medication

All concomitant medications for any conditions and changes in concomitant medications and dosages for RA will be documented in the eCRF. Participants should continue with the same concomitant medication as prior to randomization. Any co-medication with a csDMARD should be kept stable throughout the study, but tapering and termination due to AE is permitted. Flares leading to major changes in the concomitant treatment as defined in Section 3 will lead to classification as a disease flare (primary endpoint of the study). Short courses of corticosteroids for acute medical conditions other than RA (for example asthma and allergy) are permitted and will be recorded. Participants can receive intra-articular injections in one swollen joint at each visit; more than one injection at one visit will be regarded as a major change in medication and lead to classification as flare (primary endpoint). NSAIDs are permitted for use at any time during the study. NSAID doses may be increased or tapered according to clinical response. The choice and dosage of NSAIDs will be at the discretion of the treating rheumatologist and should be recorded in the eCRF. Participants who experience a flare can receive concomitant medication or switch therapy as needed.

The following concomitant medications are prohibited:

- bDMARD such as other TNFi, interleukin inhibitors, B- or T cell inhibitors
- tsDMARD such as Janus Kinase Inhibitors
- Other immunosuppressants than corticosteroids including but not limited to calcineurin inhibitors, cyclophosphamide, mycophenolate mofetil

7. Discontinuation of Study Intervention and Participant Discontinuation/Withdrawal

7.1. Discontinuation of Study Intervention

In rare instances, it may be necessary for a participant to permanently discontinue study intervention. If study intervention is permanently discontinued, the participant should, if at all possible, remain in the study to be evaluated for the primary outcome.

7.2. Participant Discontinuation/Withdrawal from the Study

- A participant may withdraw from the study at any time at the participant's own request for any reason (or without providing any reason).
- A participant may be withdrawn at any time at the discretion of the investigator for safety, behavioral, or compliance reasons.
- At the time of discontinuing from the study, if possible, an early discontinuation visit should be conducted, as shown in the SoA. See SoA for data to be collected at the time of study discontinuation and follow-up and for any further evaluations that need to be completed.
- The participant will be permanently discontinued from the study intervention and the study at that time.
- If the participant withdraws consent for disclosure of future information, the sponsor may retain and continue to use any data collected before such a withdrawal of consent.
- If a participant withdraws from the study, the participant may request destruction of any samples taken and not tested, if in accordance with local requirements and the investigator must document this in the site study records.

7.3. Lost to Follow-up

A participant will be considered lost to follow-up if the participant repeatedly fails to return for scheduled visits and is unable to be contacted by the study site.

The following actions must be taken if a participant fails to return to the clinic for a required study visit:

- The site must attempt to contact the participant and reschedule the missed visit as soon as possible, counsel the participant on the importance of maintaining the assigned visit schedule, and ascertain whether the participant wishes to and/or should continue in the study.
- Before a participant is deemed lost to follow-up, the investigator or designee must try to regain contact with the participant (where possible, telephone calls (maximum 2)), and if necessary, a certified letter to the participant's last known mailing address or local equivalent methods. These contact attempts should be documented in the participant's medical record.

- Should the participant continue to be unreachable, the participant will be considered to have withdrawn from the study.

8. Study Assessments and Procedures

- Study procedures and their timing are summarized in the SoA.
- Adherence to the study design requirements, including those specified in the SoA, is essential and required for study conduct.
- All screening evaluations must be completed and reviewed to confirm that potential participants meet all eligibility criteria. The investigator will maintain a screening log to record details of all participants screened and to confirm eligibility or record reasons for screening failure, as applicable.
- Procedures conducted as part of the participant's routine clinical management and obtained before signing of the ICF may be utilized for screening or baseline purposes provided the procedures met the protocol-specified criteria and were performed within the timeframe defined in the SoA.
- In the event of a significant study-continuity issue (e.g., caused by a pandemic), alternate strategies for participant visits, assessments, medication distribution and monitoring may be implemented by the sponsor or the investigator, as per local health authority/ethics requirements.

8.1. Administrative General, Biobank and Baseline Procedures

A screening evaluation should be performed prior to or at the same day as the inclusion visit.

The following procedures have to be completed before inclusion:

- Signing the informed consent form
- A formal assessment of the eligibility criteria

8.1.1. Baseline Procedures

Informed written consent must have been given voluntarily by each participant before any study specific procedures are initiated. In addition to the assessments and procedures performed at a regular visit described in the SoA (Section 1.3), the following assessments will be performed at baseline:

Study nurse/investigator assessments:

- Demographics (sex, birth date, and ethnic origin)
- Tobacco use
- Medical history (diagnosis, disease related previous therapy including both biological and non- biological disease modifying treatment with time for initiation and termination and reasons for discontinuation if known to the participant, duration of SC TNFi use, non-RA related medical and surgical history)
- Height and weight

8.1.2. Biobank Samples

Full blood samples (one 4 ml test tube) will be collected from all participants at the baseline visit and sent to the Department of Medical Biochemistry at Oslo University Hospital Radiumhospitalet, Norway, for biobanking. At the end of the inclusion period the samples will be transferred to a study specific biobank at Diakonhjemmet Hospital. Optionally, samples can be stored locally at the participating centers.

Participants at Diakonhjemmet Hospital only, will additionally donate samples (full blood, serum and plasma) to a study specific biobank at all onsite visits (baseline, 4, 8, 12, 18 months, early discontinuation visits and extra visits). The estimated total volume for biobank samples at each visit for these patients is 22 ml. All samples will be stored in suitable tubes and boxes designed to endure long-term storage and in a certified biobank below -70 °C. The samples will be stored until 31.12.2037 and remaining samples will thereafter be destroyed. The samples from the biobank will be used for research purposes only. Some analyses might take place in other countries than Norway including but not limited to the Netherlands, Sweden, Austria, Great Britain, Iceland, and the United States of America. These samples will be handled pseudonymised, the sample will be marked with the study ID. The laboratory receiving the samples will only have access to the study ID. The patient identification list will be stored locally at each study center.

Genetic assessments are described in Section 8.6.

8.2. Efficacy Assessments

Planned time points for all efficacy assessments are provided in the SoA (Section 1.3).

8.2.1. Assessment of Disease Activity

Patient Global Assessment of Disease Activity (PGA) (48)

PGA is measured on a 100 mm VAS according to the question: “Considering all the ways your arthritis affects you, rate how well you are doing on the following scale”, with 0 = best and 100 = worst (48-50). See Appendix 5. Approved versions in the primary language of each country will be used.

Evaluator Global Assessment of Disease Activity (EGA)

EGA is measured on a NRS according to the question ‘Please rate the patient’s overall (global) disease activity’, with 0 = best and 10 = worst (49). See Appendix 6. Approved versions in the primary language of each country will be used.

Inflammation assessment by biochemical parameters

Inflammation is measured by CRP and ESR will be recorded at all onsite visits. These tests will be analyzed at the local laboratory according to hospital procedures.

Disease Activity Score using 28 joints C-reactive protein (DAS28-CRP)

The DAS28-CRP composite score includes the 28 tender and swollen joint counts, CRP and a PGA (on a 0-100mm VAS). The DAS28-CRP is calculated as follows:

$$\text{DAS28-CRP} = 0.56*\sqrt{(\text{tender joints 28})} + 0.28*\sqrt{(\text{swollen joints 28})} + 0.36*\ln(\text{CRP mg/L}) + 0.014*\text{PGA} + 0.96$$

High disease activity is defined as a DAS28-CRP value > 5.1 , moderate disease activity as DAS28-CRP $> 3.2 - 5.1$, low disease activity as a DAS28-CRP-value of $2.6 - 3.2$, and remission as DAS28-CRP < 2.6 (50). See Appendix 7.

44 joint count

44 joint count are included in the original DAS and in addition to the joints included in DAS28 it includes the MTP joints and the sternoclavicular joints for a more comprehensive valuation of the participants' joints (51). See Appendix 8.

ACR/EULAR remission criteria

The ACR/EULAR remission criteria defines a patient in remission when either a) the patient is in Boolean 2.0 remission with each of the variables TJC, SJC and CRP having a value of ≤ 1 and PGA having a value ≤ 2 (PGA on a VAS scale 100mm/10, CRP in mg/dl) OR b) the SDAI score is ≤ 3.3 (52).

Simple disease activity index (SDAI) and Clinical disease activity index (CDAI)

The SDAI and CDAI have been developed to provide physicians and patients with simple and more comprehensible instruments for assessment of disease activity in RA. CDAI is the only composite index that does not incorporate an acute phase response and can therefore be used to conduct a disease activity evaluation essentially anytime and anywhere (49).

The formula for SDAI is: swollen joints 28 + tender joints 28 + (PGA(VAS 0-100)/10) + EGA(NRS 0-10) + (CRP (mg/dL)/10).

The formula for CDAI is: swollen joints 28 + tender joints 28 + (PGA (VAS 0-100)/10) + EGA (NRS 0-10).

See Appendix 9 and 10. Approved versions in the primary language of each country will be used.

Patient Reported Outcome Measures (PROMs)

All PROMS will be collected by the eCRF module ViedocMe. If the patients do not respond to the questionnaires, two reminders will be sent out. Approved versions of the questionnaires in the primary language of each country will be used.

Rheumatoid Arthritis Flare Questionnaire (RA-FQ)

The RA-FQ was developed by the Omeract group to identify and measure flares in patients with RA. It encompasses pain, physical impairment, fatigue, stiffness, and participation, and

the score is calculated as the sum of responses for the 5 items (maximum 50) (39, 53). See Appendix 11.

Rheumatoid Arthritis Impact of Disease (RAID) score

The RAID questionnaire was developed by EULAR as a patient-derived composite score. It includes seven domains with the following relative weights: pain (0.21), functional disability (0.16), fatigue (0.15), emotional well-being (0.12), sleep (0.12), coping (0.12) and physical well-being (0.12) each rated on an NRS (0-10). The rates of each domain are weighted and summed to form a score in the range of 0-10 (54). See Appendix 12.

Modified Heath Assessment Questionnaire (MHAQ)

The Stanford Health Assessment Questionnaire (HAQ) was introduced in the 1980s and is now widely used in evaluation of physical function in patients with inflammatory joint diseases (IJD). A shortened version of the HAQ, the MHAQ reduced the number of items from 20 in the original HAQ to eight, and improved the feasibility in clinical practice. Each item is scored on a categorical 0-3 scale and the sum score is divided by 8 to form the MHAQ score 0.0 to 3.0 (55). See Appendix 13.

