2.3.3. Overall Benefit Risk Conclusion

Considering the measures taken to minimize risk to the participants in this study, the potential risks identified in association with proactive TDM are justified by the anticipated benefits that may be afforded to patients with RA.

3. Objectives and Endpoints

Objectives	Endpoints	Assessments
Primary		
To assess whether proactive TDM is superior to standard of care in order to maintain sustained disease control without flares in patients with RA treated with SC TNFi.	
Sustained disease control over the follow-up period of 18 months without flare, with flare defined as either of the following:
 
A combination of an increase in Disease Activity Score using 28 joints- C-reactive protein (DAS28-CRP) > 1.2, or > 0.6 if DAS28-CRP ≥ 3.2, AND ≥ 2 swollen joints on examination of 44 joints
 
Consensus between participant and physician that disease flare has occurred, leading to a major change in treatment*
 
*A major change in treatment includes switching to another biological disease-modifying anti-rheumatic drug (bDMARD) or targeted synthetic disease-modifying anti-rheumatic drug (tsDMARD), adding a conventional synthetic disease-modifying anti-rheumatic drug (csDMARD), increasing the dose of a concomitant csDMARD, i.e., methotrexate increased by ≥ 5 mg/week, adding or increasing systemic glucocorticoids (per orally, intravenous, or intramuscular), and receiving more than one intra articular glucocorticoid injection at one visit. If the dose of TNFi is increased for clinical reasons (Standard of care group), this should also be regarded as a major change in treatment.
	
 • DAS28-CRP • Joint count of 44 joints

	Subgroup analyses of the primary endpoint according to each TNFi type (if more than one TNFi type will be included)	
Secondary		

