5.1. Inclusion Criteria

Participants are eligible to be included in the study only if *all* of the following criteria apply:

1. A clinical diagnosis of RA
2. ≥ 18 and < 75 years of age at screening
3. On stable therapy with standard dose of a SC TNFi (adalimumab) for a minimum of 3 months and a maximum of 24 months
4. In low disease activity or remission (DAS28-CRP < 3.2) and indication for continuation of treatment according to the treating physician
5. Subject capable of understanding and signing an informed consent form

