8.2.2. Definition of Flare

A flare is defined as a combination of an increase in DAS28-CRP of 1.2 units, or 0.6 if DAS28-CRP \geq 3.2, AND at least 2 swollen joints on examination of 44 joints (39, 40, 53).

If a participant does not fulfil the formal definition, but experiences a clinically significant worsening, according to both the investigator and participant, that leads to a major change* in treatment, this should be considered as a flare but be recorded separately in the eCRF.

*A major change in treatment includes:

- Switching to another bDMARD or a tsDMARD
- Adding a csDMARD
- Increasing the dose of a concomitant csDMARD
- Adding or increasing systemic glucocorticoids (per orally, intravenous or intramuscular)
- Receiving more than one intra-articular glucocorticoid injection at one visit
- Shortening the interval of the SC TNFi for clinical reasons (Standard of care group)

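### The printed DAS28-CRP formula takes ln(CRP) with no offset, so it has no value at CRP 0 and distorts low-CRP scores used for entry and flare; the SDAI CRP term mixes mg/dL with a divisor for mg/L

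*Protocol*

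**What the plan says.** Protocol section 8.2.1 introduces the score with "The DAS28-CRP is calculated as follows" and gives 0.56 × √TJC28 + 0.28 × √SJC28 + the CRP term + 0.014 × PGA + 0.96. The CRP term is "0.36*\ln(\text{CRP mg/L". No rule for a CRP of 0 or below detection stands beside it. On CRP and ESR the same section says: "These tests will be analyzed at the local laboratory according to hospital procedures".

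The score is used in three places:

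- **Entry** (section 5.1, criterion 4): "In low disease activity or remission (DAS28-CRP < 3.2".
- **Formal flare** (sections 3 and 8.2.2): a rise above 1.2, or above 0.6 if DAS28-CRP is at least 3.2, "AND at least 2 swollen joints on examination of 44 joints".
- **Choice of flare threshold**: the level 3.2 decides which of the two rises applies.

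Section 8.2.2 adds a consensus route: "If a participant does not fulfil the formal definition, but experiences a clinically significant worsening" and treatment undergoes a major change, the event also counts. In section 3 the two routes are alternatives, "with flare defined as either of the following".

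For SDAI, section 8.2.1 ends the formula with "EGA(NRS 0-10) + (CRP (mg/dL)/10". The Boolean remission rule in the same section uses CRP in mg/dl with no divisor, and sets SDAI remission at 3.3 or below. Appendices 7 (DAS28-CRP) and 9 (SDAI) are withheld from the public version.

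**The concern.** The logarithm of zero does not exist, and ln(CRP) falls without bound as CRP approaches zero. Participants enter in remission or low disease activity, so low CRP values are plausible, and this is where the printed formula is most sensitive. Compared with a formula that has a positive offset inside the logarithm, it gives a lower level and a larger rise from a low starting CRP. The lower level can admit a participant or keep a visit below 3.2; the larger rise can create a formal flare. Because CRP is run locally, sites with different low-end reporting could also score the same patient differently.

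The SDAI term is a separate unit error. Since 1 mg/dL = 10 mg/L, a term meant to be CRP in mg/dL becomes ten times too small if that value is again divided by 10. This touches only secondary endpoints, which section 9.1.1 makes descriptive, but it can misclassify remission.

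**Working it through.** The protocol states no worked score, so there is no figure to reproduce. The check evaluates the printed formulas. **Offsets, floors and participant values below are assumptions; the protocol gives none.**

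**Set-up.** Score = 0.56√TJC + 0.28√SJC + 0.36 ln(CRP + o) + 0.014 PGA + 0.96, with o = 0 as printed. A floor f replaces CRP by max(CRP, f). Entry cannot occur at 3.2 or above, so the 3.2 condition in the flare rule is read as the level at the flare visit.

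**Behaviour of the printed term.** At CRP 0 it is undefined. Each halving of CRP changes it by 0.36 × ln 2 = 0.250. With no tender or swollen joints and PGA 0, the score is negative below CRP = exp(−0.96/0.36) = 0.069 mg/L.

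**Shortfall in level**, 0.36 × ln((CRP + o)/CRP):

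| CRP (mg/L) | o = 0.1 | o = 0.5 | o = 1 |
|---|---|---|---|
| 0.5 | 0.066 | 0.250 | 0.396 |
| 1 | 0.034 | 0.146 | 0.250 |
| 3 | 0.012 | 0.055 | 0.104 |
| 5 | 0.007 | 0.034 | 0.066 |
| 10 | 0.004 | 0.018 | 0.034 |

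**Example A, formal flare gained.** TJC 0, SJC 0, CRP 0.5, PGA 10 changes to TJC 0, SJC 2, CRP 5, PGA 15.

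- Non-CRP rise: 0.28 × √2 + 0.014 × 5 = 0.466.
- As printed: 0.466 + 0.36 × ln(5/0.5) = 1.295 (0.850 to 2.145). This exceeds 1.2.
- Rise with an offset: 1.236 (o = 0.1), 1.080 (0.5), 0.965 (1). It equals 1.2 at o of about 0.173.
- With a floor it equals 1.2 at f = 5/exp((1.2 − 0.466)/0.36) = 0.651 mg/L. A floor at or below the starting 0.5 mg/L changes nothing.

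**Example B, formal flare missed.** TJC 1, SJC 0, CRP 1, PGA 50 changes to TJC 4, SJC 2, CRP 1, PGA 50.

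- Rise: 0.956 for every offset, between 0.6 and 1.2, so the level decides.
- Second level as printed: 1.12 + 0.396 + 0 + 0.70 + 0.96 = 3.176, below 3.2, so no formal flare.
- Second level with an offset: 3.210 (o = 0.1), 3.322 (0.5), 3.426 (1). It reaches 3.2 at o of about 0.069. A floor at or below 1 mg/L changes nothing.
- The same second state at screening is eligible as printed and ineligible from that offset upwards.

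**Example C, a higher CRP.** TJC 4, SJC 2, CRP 3, PGA 22 at screening gives 1.12 + 0.396 + 0.396 + 0.308 + 0.96, which is 3.179 before rounding of the terms (eligible). With o = 1 it is 3.283 (ineligible).

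**SDAI.** CRP 20 mg/L = 2 mg/dL. As printed it adds 2/10 = 0.2; in mg/dL undivided it adds 2.0. With no swollen or tender joints, PGA 15 mm and EGA 1:

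- As printed: 0 + 0 + 1.5 + 1 + 0.2 = 2.7, remission.
- With CRP in mg/dL: 0 + 0 + 1.5 + 1 + 2.0 = 4.5, not remission. CRP of 2 mg/dL also fails the Boolean limit of 1, so the overall remission status changes.

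**The case against.** The strongest reply is that the formula is incomplete rather than wrong. It is defined for every positive CRP, nothing says a laboratory reports exactly 0, and a reporting limit stops the fall at low values. Values below detection are a data-handling matter that a SAP may cover. If low values are set to the reporting limit, examples A and B both disappear at a limit of about 1.07 mg/L: A has already stopped at 0.651, and B reaches 3.176 + 0.36 × ln 1.07 = 3.200. The correct formulas may also stand in the withheld appendices.

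Part of this stands. A reporting limit does bound the effect in real data; if nothing below about 3 mg/L is reported, the level gap is at most about 0.10 for offsets up to 1. It does not remove the problem: example C changes eligibility at CRP 3 mg/L. Nor is this missing detail. The protocol states a formula as the way the score is calculated, and that formula fails on a possible input. A withheld appendix does not correct the body text, though it does mean that the formula in use is unknown.

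The consequences are also limited. CRP alone cannot make a formal flare, because two swollen joints are required. A missed formal flare such as B may still be counted by consensus if treatment is changed. That protection runs one way only: the routes are alternatives, so consensus cannot remove a flare gained as in A. On SDAI, the Boolean rule is a different rule; its undivided mg/dl supports the unit reading without proving it.

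**Conclusion.** Both formulas are wrong as printed in the public protocol and should be corrected. The failure of DAS28-CRP at CRP 0 and its lack of a lower bound follow from the printed text alone. The size does not: it rests on an assumed offset of 0.1 to 1, and the examples were chosen near cut-offs. On those assumptions the printed level is low by 0.03 to 0.25 at CRP 1 mg/L and by 0.01 to 0.07 at 5 mg/L, enough to change eligibility or formal flare status only for borderline participants. The protocol gives neither the CRP distribution nor a reporting limit, so the share affected cannot be stated. There is no claim of bias between arms, and no evidence that any score has been computed wrongly. The SDAI error is tenfold in the CRP term but confined to descriptive secondary endpoints.

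**What to change.** In section 8.2.1, correct the CRP term of DAS28-CRP so that it is defined at zero, taking the exact form from the cited index and Appendix 7. ln(CRP + 1) with CRP in mg/L is one candidate, but it is an assumption to be confirmed there. Write the SDAI term either as CRP in mg/dL with no divisor or as CRP in mg/L divided by 10, and reconcile it with Appendix 9. Then check which formulas the eCRF uses. The cost is two corrected formulas and one calculation check. Stored scores need re-deriving only if the printed versions were programmed, and no new data are needed.
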